## **STUDY PROCEDURES**

### **Enrollment and Screening**

[figure not shown]
During the first visit, the research staff will screen the subject for eligibility to participate. The inclusion/exclusion criteria will be reviewed, the subject's medical history, an examination of the subject's skin in the treatment areas will be conducted.

The subject will review the informed consent form and the study will be explained to the subject including all risks, potential benefits, procedures, visit requirements, and other alternative treatment options. If the subject qualifies and wishes to participate they will complete the ICF with a signature and date. The original will be retained with subject's records and a copy will be provided to the subject.

The following measurements will be performed and recorded at the specified times throughout the study.

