### **Screening**

1. ICF - Prior to any study procedures, informed consent will be obtained. When the subject fully understands the possible benefits and risks of the study, the subject will be asked to sign and date the informed consent form (ICF). The subject will be given a copy of the signed ICF.
2. Subject ID - subjects will be assigned a study subject ID number.
3. Medical History - A medical history will be obtained to determine if the subject meets the study criteria, including a list of all prescribed and over the counter medications taken within the previous 6 months will be recorded.
4. Skin Exam - The subject will undergo a routine skin exam to determine if they meet the study criteria including the presence of fatty tissue deposits in the treatment area.
5. BMI – the volunteers’ height and weight will be taken for calculation of BMI.
6. Pregnancy Screen - Subjects who are capable of becoming pregnant will undergo a urine pregnancy test. This will be repeated prior to all treatments, and at the end of the study (last FU visit/ 12wk FU). If the Screening and Treatment procedures are not conducted on the same day, the urine pregnancy test will be repeated on the first treatment day.
7. Scheduling: Subjects will be scheduled to return for the baseline and first treatments visit within 14 days following the screening visit. It is preferable the baseline procedures and Tx.1 will be conducted immediately after the Screening visit.

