### **Informed Consent**

The Study Personnel will obtain written Informed Consent prior to the subject's participation in any study procedures. The Study Personnel will inform the subjects of the experimental procedure to be utilized and assure the subjects that their decision regarding participation in the study will have no bearing on the quality of medical care received and that their decision whether to participate in the study is strictly voluntary.

During the initial interview, the subject will be assured that they are free to change their mind and will be allowed to participate in the study or withdraw from the study with no adverse effect on their standard medical care.

 Syneron Medical Ltd. Confidential	Clinical Study to Evaluate the Safety and Efficacy of the SlimShape Device for Abdominal Fat and Circumference Reduction			
	Protocol #	DHF22621	Rev. Date	October 8, 2017

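### Enrollment and Screening makes the consent signature depend on qualifying, while Screening and Informed Consent require it before any study procedure

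*Combined protocol and SAP*

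**What the plan says.** Four places in the protocol state when consent is obtained or what it depends on.

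- **Study Procedures, Enrollment and Screening.** The section opens with eligibility: "During the first visit, the research staff will screen the subject for eligibility to participate". It names the review of the criteria, the medical history and the skin: "an examination of the subject's skin in the treatment areas will be conducted". The next paragraph covers the consent form and the explanation of the study, and ends: "If the subject qualifies and wishes to participate they will complete the ICF with a signature and date".
- **Pre-Treatment Procedures, Screening.** This is a numbered list. Item 1: "Prior to any study procedures, informed consent will be obtained". Item 2: "subjects will be assigned a study subject ID number". Item 3 is the medical history. Item 4: "The subject will undergo a routine skin exam to determine if they meet the study criteria". Items 5 and 6 are BMI and the pregnancy screen.
- **Administrative Procedures, Informed Consent.** "The Study Personnel will obtain written Informed Consent prior to the subject's participation in any study procedures".
- **Inclusion Criteria, item 1.** Signed consent is itself a condition of eligibility.

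The schedule in Appendix I (Table 3) lists the consent process above eligibility screening, with both marked in the same visit column.

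**The concern.** A coordinator who works from Enrollment and Screening would find out whether a person qualifies, and only then ask for a signature. One who works from the Screening list would ask for the signature first. For the history and the skin examination, these instructions cannot both be obeyed.

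What is at stake is participant protection. The examined area is the abdomen, and the history has to cover exclusions such as HIV status, hepatitis and cancer (Exclusion Criteria, items 2 and 3). Collecting this before signature is what the Screening and Informed Consent sections rule out. The section on Ethics and Good Clinical Practice also commits the study to the federal rules on informed consent and to GCP. Pre-Treatment Procedures expects screening, baseline and treatment to fall in one visit, so the order within that visit needs to be stated once and without conflict.

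**Working it through.** No arithmetic applies. The documents give no screening count or screen-failure rate, and the point uses no alpha, power, effect size or N. The check is a comparison of the texts.

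| Step | Enrollment and Screening | Screening (numbered list) |
|---|---|---|
| Criteria review | Described before the consent paragraph | No separate step; history and skin exam serve it, after the ICF |
| Medical history | Described before the consent paragraph | Item 3, after the ICF |
| Skin examination | Described before the consent paragraph | Item 4, after the ICF |
| Explanation of the study | Before signature | Within item 1, before signature |
| ICF signature | Conditional on qualifying | Item 1, before any study procedure |
| Subject ID | Not mentioned | Item 2 |
| BMI, pregnancy test | Not mentioned | Items 5 and 6 |

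1. *Does Enrollment and Screening really put screening first?* It has no step numbers and no explicit linking word between its two paragraphs, so paragraph order alone would be weak evidence. The conditional clause is stronger. If the signature depends on qualifying, qualification must be judged before the signature, and the only means of judging it that the section describes are the criteria review, the history and the skin examination.

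2. *Are these study procedures or informal pre-screening?* The Screening list names the history and the skin exam as screening steps and ties both to whether the subject meets the study criteria. They therefore fall under its item 1 and under the Informed Consent section, which requires staff to "obtain written Informed Consent prior to the subject's participation in any study procedures".

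3. *Can a person qualify before signing?* Not fully. Signed consent is inclusion criterion 1, and Number of Subjects enrolls only people who meet all inclusion criteria. Signing only after qualifying is therefore circular.

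4. *How far does the conflict reach?* It covers the criteria review, the history and the skin examination. Enrollment and Screening does not mention BMI or the pregnancy test, so the point does not extend to them.

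5. *Does any analysis change?* No. The planned comparisons are of follow-up with baseline in treated subjects. None uses the number screened.

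**The case against.** The strongest reply is that the rule is clear wherever the protocol is most specific. The numbered Screening list, the dedicated Informed Consent section and inclusion criterion 1 all point to signature first, and the row order of Table 3 agrees. Enrollment and Screening is an unnumbered narrative, and most sites would probably follow the numbered list. The figure in that section and the flow-chart (Figure 4) are not shown in the text available, and the consent pages were removed, so what they say about the order could not be checked.

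Much of this stands. It shows which order the protocol intends and makes the correction uncontroversial. It does not remove the conflict, because the conditional clause is an operative instruction about when to sign, and no figure could cancel it.

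A reader might go further and infer that signing late loses the screening denominator, or that results from people who fail cannot be kept. The documents do not support either inference:

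- The plan defines no screening denominator, screen-failure category or screening log under either order, so the wording removes nothing that the plan had. A site could still count the people it screens.
- No section states a retention rule for unsigned screening results.
- It is true that a person who fails before signing would have no signed form and, if IDs are assigned as in the Screening list, no subject ID. But anyone who declines to sign lacks both under the Screening list as well, so the consent order does not decide this.
- Selection into the sample is not otherwise invisible. The protocol gives 10 inclusion and 21 exclusion criteria, and Demography and Baseline Measurements provides for a descriptive presentation. These do not replace a log, but they do describe who was selected.

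**Conclusion.** The inconsistency is real and should be corrected. Enrollment and Screening makes signature conditional on qualifying, whereas Screening and Informed Consent require signature before any study procedure, and inclusion criterion 1 makes it part of eligibility. A site that follows the first text takes a history and examines the skin without consent and so breaches the other two.

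The conclusion rests on reading the conditional clause in its ordinary sense and on treating the history and skin exam as study procedures, as the Screening list does. The reach is any person screened at a site that follows Enrollment and Screening. How many people or sites that would be cannot be estimated from the documents. The effect on endpoints, tests and sample size is nil, so this is a matter of participant protection and internal consistency. It is not a flaw in the analysis.

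**What to change.** Reconcile the sections by rewriting Enrollment and Screening in the order of the Screening list: explain the study, obtain the signed and dated ICF, assign the subject ID, carry out the history, skin exam and remaining screening steps, and then decide eligibility. Delete the clause that makes qualifying a condition for signing. Check that the figure in that section and the flow-chart in Figure 4 show the same order.

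The cost is a few sentences of protocol text. No procedure or visit is added. Some people will sign and then fail screening, which is the ordinary consequence of consenting first.

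A screening log with reasons for failure is an optional, separate suggestion. It could help readers of a one-arm study see how the sample arose, but this correction does not depend on it, and a log limited to consented subjects would still omit those who decline to sign.

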**Table 2 – Clinical Evaluation Measurements and Tools**

Measurement	When to conduct	Method
Height	Baseline	Scale
Weight	Prior to all treatments (Tx.1, Tx.2 & Tx.3), and at all follow-ups visits (4wk FU, 8wk FU & 12wk FU)	Scale
BMI		Calculation
Fat thickness UltraSound measurements	Baseline, Prior to Tx.3, and at all follow-ups visits (4wk FU, 8wk FU & 12wk FU)	Ultrasound device
Fat thickness Caliper measurements	Prior to all treatments (Tx.1, Tx.2 & Tx.3), and at all follow-ups visits (4wk FU, 8wk FU & 12wk FU).	Calibrated Caliper
Circumference measurements		Standardized circumference measuring tape
Photographs		Standardized digital photographs
Urine pregnancy test	Prior to all treatments (Tx.1, Tx.2 & Tx.3), and at the last follow-up visit (12wk FU)	Urine pregnancy test
Immediate response assessment	Immediately after each treatment (Tx.1, Tx.2 & Tx.3)	Post Treatment Side Effect Severity Scale (Table 4)
Investigator satisfaction	At all follow-up visits (4wk FU, 8wk FU and 12wk FU)	Satisfaction Questionnaire (Table 6)
Subject satisfaction		Satisfaction Questionnaire (Table 6)
Subject improvement assessment		Improvement Questionnaire (Table 5)
Safety	During treatment and throughout study.	Examination of skin in the treated area, interview subjects, Adverse Events form, Occurrence and Severity Ratings, as well as relation to treatment, action taken and outcome

**Figure 4: Study Flow-Chart (Visits at the Clinic)**

 Syneron Medical Ltd. Confidential	Clinical Study to Evaluate the Safety and Efficacy of the SlimShape Device for Abdominal Fat and Circumference Reduction			
	Protocol #	DHF22621	Rev. Date	October 8, 2017

### **Pre-Treatment Procedures**

It is expected that the screening and baseline procedures will be conducted during the same visit as the treatment (prior to the treatment). The treatment visit procedures will take up to 1.5 hours.

### **Screening**

1. ICF - Prior to any study procedures, informed consent will be obtained. When the subject fully understands the possible benefits and risks of the study, the subject will be asked to sign and date the informed consent form (ICF). The subject will be given a copy of the signed ICF.
2. Subject ID - subjects will be assigned a study subject ID number.
3. Medical History - A medical history will be obtained to determine if the subject meets the study criteria, including a list of all prescribed and over the counter medications taken within the previous 6 months will be recorded.
4. Skin Exam - The subject will undergo a routine skin exam to determine if they meet the study criteria including the presence of fatty tissue deposits in the treatment area.
5. BMI – the volunteers’ height and weight will be taken for calculation of BMI.
6. Pregnancy Screen - Subjects who are capable of becoming pregnant will undergo a urine pregnancy test. This will be repeated prior to all treatments, and at the end of the study (last FU visit/ 12wk FU). If the Screening and Treatment procedures are not conducted on the same day, the urine pregnancy test will be repeated on the first treatment day.
7. Scheduling: Subjects will be scheduled to return for the baseline and first treatments visit within 14 days following the screening visit. It is preferable the baseline procedures and Tx.1 will be conducted immediately after the Screening visit.

### **Baseline**

1. Photography – Baseline photographs will be obtained using a consistent camera and subject placement settings with a digital imaging system.
2. BMI – the subject weight and height will be taken if baseline visit occurs on a different day than the screening visit.

SYNERON CANDELA Syneron Medical Ltd. Confidential	Clinical Study to Evaluate the Safety and Efficacy of the SlimShape Device for Abdominal Fat and Circumference Reduction			
	Protocol #	DHF22621	Rev. Date	October 8, 2017

## Measurements

[figure not shown]
### Measure the Fat Thickness at the Treated Area – Calibrated Caliper

Assess fat thickness at treatment area prior starting the treatment using calibrated caliper.

### Measure the Fat Thickness at the Treated Area – Ultrasound Imaging Device

Ultrasound Imaging (USI) provides a valid way for measuring fat thickness using known interfaces observed in any individual. USI relies on the ability to recognize different sub-skin interfaces and correctly identifying them, such as the **dermis** and the **subcutaneous fat layer** interfaces.

- Treated area is defined below the sternum and above the iliac. Mark the rectangle of the treated area with white pencil.
- Measure 2-4 cm from each edge of the umbilicus (superiorly and inferiorly) and 1.5-3 cm medially and laterally from the ends of these points (as **illustrated in Figure 5, white lines**). Make sure that the measurement points selected are at least 1 cm from the edges of the treatment area (including the width of the USI transducer, **see green arrows in Figure 5**).

UR – Upper Right measurement point, UL – Upper Left measurement point, LR – Lower Right measurement point, LL – Lower Left measurement point

**Figure 5: Ultrasound Measurements Points**

[figure not shown]
- Mark the treated area and the measurements points on the transparency, to ensure measurement of the same point in each subsequent visit.

- d) Ultrasound measurements should be obtained from the edges of the measurement points, laterally (see **Figure 5 above, yellow dashed lines**).
- e) Place the applicator on the skin surface at angle of 90° (located the applicator under the measurement point line for consistency).
- f) Measurement should include all the area between the dermis and end of the fat tissue fascia. At least 2 measurements should be done in each measurement point.

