**TABLE 1- STUDY SYNOPSIS**

Proprietary Name	SlimShape device
Design	
Prospective, one arm, baseline-controlled, clinical study for the evaluation of the SlimShape device for non-invasive abdominal fat and circumference reduction.
 
Study subjects will undergo SlimShape treatments on the abdominal area

Study Population	Up to 120 healthy adult volunteers, seeking for noninvasive abdominal fat and circumference reduction, male and females, 18 to 60 years of age from up to 10 investigational sites.
Treatment and Duration	
Eligible subjects will receive up to 3 bi-weekly treatments (2 weeks interval) with the SlimShape device utilizing the SlimShape Applicator Belt according to the study protocol.
 
The subject will return for 3 follow up visits: four weeks (4wk FU), eight weeks (8wk FU) and 12 weeks (12wk FU) after the last treatment.
 
Each subject will be enrolled for total expected study duration of up to 16 weeks.

Objective	The objective of this trial is to evaluate the safety and efficacy of the SlimShape device utilizing the SlimShape Applicator Belt for abdominal non-invasive fat and circumference reduction
Primary Objective	Statistically significant abdominal fat reduction post SlimShape treatments at 12 weeks follow-up (12wk FU) versus baseline
Primary Safety Objective	Evaluate the safety of the treatment with the SlimShape device utilizing the SlimShape Applicator Belt during all study
Secondary Objectives	
 
1. Statistically significant abdominal fat reduction post SlimShape treatments as measured by Ultrasound device at Pre Tx.3, 4 weeks, and 8 weeks follow-up (4wk FU and 8wk FU) versus baseline
 
2. Statistically significant abdominal fat reduction post SlimShape treatments as measured by calibrated Caliper device at Pre Tx.3, 4 weeks, 8 weeks and 12 weeks follow-up (4wk FU, 8wk FU and 12wk FU) versus baseline
 
3. Statistically significant abdominal circumference reduction post SlimShape treatment/s at Pre Tx.2, Pre Tx.3, 4 weeks, 8 weeks and 12 weeks follow-up (4wk FU, 8wk FU and 12wk FU) versus baseline
 
4. Investigator satisfaction: 
Satisfaction assessment will be performed by the study investigator using a pre-defined scale questionnaire. The investigator will answer this questionnaire at each follow-up visit (4wk FU, 8wk FU and 12wk FU)
 
 

Protocol #

DHF22621

Rev. Date

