## 5. Subject improvement and satisfaction:

Improvement and satisfaction assessment will be performed independently by the subject using a pre-defined scale questionnaire. The subjects will answer this questionnaire at each follow-up visit (4wk FU, 8wk FU and 12wk FU)

 Syneron Medical Ltd. Confidential	Clinical Study to Evaluate the Safety and Efficacy of the SlimShape Device for Abdominal Fat and Circumference Reduction			
	Protocol #	DHF22621	Rev. Date	October 8, 2017

Efficacy Endpoints	Primary and secondary objectives will be measured using the next efficacy endpoints: 
 
1. Fat thickness measurements using Ultrasound device
 
2. Fat thickness measurements using Caliper
 
3. Circumference measurements of the abdominal area using Measuring Tape
 
4. Investigator satisfaction using a pre-defined scale
 
5. Subject improvement and satisfaction using a pre-defined scale
 
6. Photography
 

Safety Endpoints	
 
1. The number, severity and type of any adverse event recorded throughout the study and post treatment (immediate and delayed response)
 

Statistical Methods	Descriptive statistics will be used to present changes in the assessments along the study course. Circumference measurements and subject assessments' and satisfaction data will be analyzed using two-tailed Wilcoxon Signed Rank test and/or paired t-test (alpha=0.05) to analyze the data difference from baseline and longitudinal change.

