### **Primary Objective**

Statistically significant abdominal fat reduction as measured by Ultrasound Imaging device post SlimShape treatments at 12 weeks follow-up (12wk FU) versus baseline.

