## **STUDY POPULATION**

### **Number of Subjects**

This study will be comprised of up to 120 subjects in up to ten (10) investigational sites. Subjects who meet all the inclusion and none of the exclusion criteria will be enroll.

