### **Treatment Procedure**

Subjects will receive treatments with SlimShape device utilizing the SlimShape Applicator Belt on the anterior abdomen.

Prior to each treatment measurements of weight, fat thickness (by Caliper & Ultrasound), and abdominal circumference will be done according to the references from the enrollment visit

 Syneron Medical Ltd. Confidential	Clinical Study to Evaluate the Safety and Efficacy of the SlimShape Device for Abdominal Fat and Circumference Reduction			
	Protocol #	DHF22621	Rev. Date	October 8, 2017

(Baseline/ prior to Tx.1). Only patients who are eligible for treatment will be allowed to undergo the SlimShape procedure.

Enrolled subjects will undergo up to 3 successive (according to investigator decision) bi-weekly (2 weeks interval) treatments (Tx.1, Tx.2 and Tx.3). Additional three (3) visits in the clinic will be occurred to follow-up the abdominal fat and circumference reduction at visits 4, 5 and 6 (4 weeks, 8 weeks and 12 weeks following last treatment).

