### **Case Report Forms**

Paper case report forms will be used in this trial. All protocol-required information collected during the study must be entered in the appropriate field of the case report form (CRF). The investigator, or designated representative, should complete the appropriate CRF fields as soon as possible after information is collected. The information must match the information that exists as source documents in the clinic chart, hospital chart, and/or investigator's files. An explanation should be given for all missing data.

It is the investigator's responsibility to assure the accurate completion, review, and approval of all CRFs and the timely completion and submission of all adverse event forms.

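### No masking of the ultrasound reader to visit or earlier values is specified, so in this one-arm trial a systematic tendency to read thinner at follow-up would count in full as device effect

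*Combined protocol and SAP*

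**What the plan says.** The Study Synopsis describes a "Prospective, one arm, baseline-controlled, clinical study", so each subject's own baseline is the only comparator. The Primary Objective is "Statistically significant abdominal fat reduction as measured by Ultrasound Imaging device post SlimShape treatments at 12 weeks follow-up (12wk FU) versus baseline". It sets no minimum change in millimetres.

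The ultrasound part of the Measurements section says that the method depends on recognising and correctly identifying tissue interfaces, so the reading involves judgement. The steps there and under Figure 5 fix four measurement points (UR, UL, LR, LL), a transparency to find them again, the probe angle and the layer limits. They also call for replicates: "At least 2 measurements should be done in each measurement point".

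These steps do not say who reads the scans, whether readings are made live or on saved images, whether earlier thickness values are withheld, or how the replicates are combined. Masking, blinding and an independent or central reader are not mentioned anywhere. The one recommendation aimed at operator error (same operator, similar hour of day) is under Measuring Circumference and does not extend to ultrasound.

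On size, "This study will be comprised of up to 120 subjects in up to ten (10) investigational sites". Subject Withdrawal and Replacement aims at no fewer than 120 completers.

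**The concern.** The location, angle, layer and replicate rules control reproducibility. They do not control expectation. Every subject is treated, and the section on potential benefits states an expectation that all treated subjects will gain something. If readers tend, on average, to place the boundaries slightly closer together at follow-up than at baseline, no control arm exists to cancel the shift, and it goes straight into the mean change. Because success is defined by significance alone, a shift just large enough to cross the 0.05 threshold would meet the primary objective even if the device did nothing.

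**Working it through.** The plan gives no power calculation, expected effect, SD of change or reader repeatability, so there is no figure of its own to reproduce. The check asks how large a purely directional reading bias must be to matter.

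**Inputs**
- n = 120 (Number of Subjects; Subject Withdrawal and Replacement). Because the enrolment figure is an upper limit, n = 60 is shown as a lower case (assumed).
- Two-sided alpha 0.05, paired t-test. This is an assumption for ultrasound: the Statistical Methods row of the synopsis names these tests and this alpha for circumference and subject assessments and assigns none to ultrasound.
- True device effect: zero.
- Bias b = 0.1, 0.2 or 0.3 SD of the change score. These sizes are assumed; the documents give none.

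**Smallest mean shift that is significant**, in SD of change: t(0.975, n−1)/√n.
- n = 120: 1.980/10.954 = 0.181 SD.
- n = 60: 2.001/7.746 = 0.258 SD.

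**Chance of a significant reduction from bias alone**: 1 − F(t(0.975, n−1)), where F is the noncentral t distribution with n−1 degrees of freedom and noncentrality b√n.

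| b (SD of change) | b√n, n = 120 | chance, n = 120 | b√n, n = 60 | chance, n = 60 |
|---|---|---|---|---|
| 0 | 0 | 2.5% | 0 | 2.5% |
| 0.1 | 1.095 | 19.1% | 0.775 | 11.5% |
| 0.2 | 2.191 | 58.4% | 1.549 | 33.1% |
| 0.3 | 3.286 | 90.3% | 2.324 | 62.8% |

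The result does not depend on the choice between the two tests. With 4,000 simulated trials of 120 subjects per bias, the Wilcoxon signed rank test gave 18.6%, 56.7% and 89.6% at 0.1, 0.2 and 0.3 SD.

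**In millimetres**, only under an assumed SD of change of 2 to 5 mm: the just-significant shift is 0.36 to 0.90 mm at n = 120 (0.181 × 2 to 0.181 × 5) and 0.52 to 1.29 mm at n = 60.

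**The case against.** The study openly declares a one-arm, baseline-controlled design, and the arithmetic above would apply to any such study of this size. It shows sensitivity to bias, not the presence of bias. A shift matters only if it runs in one direction on average across up to ten sites; random reading error does not raise the 2.5%. The protocol also makes a real effort to standardise the scan. All of this stands and limits what can be concluded. None of it supplies the missing safeguard.

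A reader might infer more than the documents support:
- **That operators place the markers live, knowing the visit.** This is plausible for scans taken in clinic at scheduled visits, but the text does not say it. The Recording section has images retrieved at monitoring visits, and the section on subjects' rights and welfare has images stored without identifiers. Whether these include ultrasound frames is unclear.
- **That earlier thickness values are consulted.** Treatment Procedure has pre-treatment measurements made "according to the references from the enrollment visit". This most naturally means positional references (the transparency and the recorded heights), and it does not concern the 12-week reading.
- **That earlier readings are in the operator's hands because** "Paper case report forms will be used in this trial". The Recording section says that the forms are retrieved at monitoring visits while source documents stay in the site's files. Nothing prevents access, but nothing shows that it happens.

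**Conclusion.** The point holds as a gap in safeguards. No masking to visit or to earlier thickness values is specified for the sole primary measurement, and in this design a directional reading bias would be counted in full as device effect. The documents do not show that such a bias occurs, so they do not support calling a future positive result false.

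In SD units, a mean shift of 0.18 SD (n = 120) or 0.26 SD (n = 60) is just significant. Biases of 0.1 to 0.3 SD would raise the chance of a spurious reduction from 2.5% to between 19% and 90% at n = 120, or between 12% and 63% at n = 60. These figures rest on the assumed test, the assumed bias sizes and a true effect of zero. The millimetre figures also rest on an assumed SD. This is a cheap improvement worth making, not a defect that invalidates the plan.

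**What to change.** Add two parts to step f) of the ultrasound instructions, before the first baseline scan, because frames not saved at baseline cannot be recovered.

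1. Carry forward only the transparency that marks the ultrasound points. Record thickness at each visit on a fresh source page, with earlier thickness values withheld from the operator. This removes anchoring on earlier values but does not hide the visit.
2. Where the device can save frames, save every frame at each point under a code with no visit label. An existing site or sponsor staff member who does not read the scans assigns and holds the codes. After a subject's 12-week visit, one existing site operator reads all of that subject's images in random order. The mean of all readings over the four points is the primary value, which also supplies the missing rule for combining replicates.

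Part 1 costs one sentence and a source page. Part 2 costs image storage, coding and re-reading time by existing staff. Neither needs an extra reader or visit. Frame acquisition (probe pressure, choice of frame) would remain unmasked, and regression to the mean, weight change and the lack of a control arm would not be addressed.
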